#### 7. SAFETY

#### 7.1 Potential risks & benefits to study participants

There is no anticipated personal safety risk associated with taking part in this study. If the research team learns of important new information that might affect patient's desire to remain in the study, he or she will be told. Appropriate precautions are in place to ensure medical and personal information is kept safe through adhering to appropriate governance regulations. Participants in both the treatment arms will be allocated a compression bandage that is used for its intended licensed purpose and that is available via standard care routes. Any adverse events will be recorded, as outlined in sections below.

Apart from being allocated to a different type of compression bandage, all patients will be commenced on a compression therapy that aims to achieve 20-30 mmHg of pressure; therefore, all patients will receive the indicated clinical care they would receive when not in the trial too. They will otherwise be cared for in exactly the same manner as they normally would. Some bandage types may be more comfortable and more effective at controlling symptoms associated with vascular pathology and this present trial aims to establish whether this holds true. Participants cannot claim payments, reimbursement of expenses or any other benefits or incentives for taking part in this research.

#### 7.2 Safety definitions

Adverse Event (AE)	Any untoward medical occurrence in a patient or other clinical investigation participant taking part in a trial of a medical device, which does not necessarily have to have a causal relationship with the device under investigation.		
	An AE can therefore be any unfavourable and unintended sign		
	(including an abnormal laboratory finding), symptom or disease		
	temporally associated with the use of the device, whether or not		
	considered related to the device.		
Serious Adverse Event	A serious adverse event is any untoward medical occurrence that:		
	- results in death		
	- is life-threatening		
	
 
requires inpatient hospitalisation or prolongation of existing hospitalisation
 
		
	
 
results in persistent or significant disability/incapacity
 
consists of a congenital anomaly or birth defect.
 
		
	Other 'important medical events' may also be considered serious if they		
	jeopardise the participant or require an intervention to prevent one of		
	the above consequences.		
	NOTE: The term "life-threatening" in the definition of "serious" refers to		
	an event in which the participant was at risk of death at the time of the		
	event; it does not refer to an event which hypothetically might have		
	caused death if it were more severe.		

#### 7.3 **Procedures for recording adverse events**

All SAEs need to be reported to the sponsor/host Trust R&D within one working day of the investigator team becoming aware of them.

The relationship of each adverse event to the trial must be determined by a medically qualified individual according to the following definitions:

- **Related**: The adverse event follows a reasonable temporal sequence from intervention. It cannot reasonably be attributed to any other cause.
- **Not Related**: The adverse event is probably produced by the participant's clinical state or by other modes of therapy administered to the participant.

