Treatment success in CVI is highly dependent on achieving high levels of patient compliance. Unfortunately, compliance rates are often poor in this population (Heinen et al , 2007). Undesirable effects of compression bandaging play a role in this. Apart from bandage slippage, the most common undesirable effects of wearing compression bandaging are skin-related. Dryness and redness of the skin are commonly reported, and pruritus develops in as many as 1 in 3 patients (Reich-Schupke et al, 2009). Unna's boot has been shown in the past to be effective at controlling pruritis in different conditions, including burns-related long-term itch (Shohrati et al, 2007). A recent study by Jonker and colleagues (2020) showed that patients deem the Andoflex TLC Calamine compression bandaging more comfortable, and less itchy, than Coban2 compression bandaging; there was also a trend towards improved healing rates with Andoflex TLC Calamine.

The aim of this pragmatic randomised, controlled, prospective trial is to determine the efficacy of two types of two-layer compression bandaging (Andoflex TLC Calamine Lite and Coban 2 Lite), with a primary outcome measure of healed ulcer at week 12. Secondary outcome measures will be other ulcer characteristics, and patient-reported quality of life.

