#### APPENDIX 2. INTERVENTION DEVIATION AND LEG ULCER INFECTION

There may be incidences where a participant may either:

- Develop a reaction to the allocated dressing/bandage
- Becomes completely non-compliant (possibly due to bandaging being uncomfortable, or eg hospital admission)
- Improve to such an extent that compression bandaging is no longer indicated.

In such instances the patient and/or clinician can opt to stop or pause treatment with the bandage in question. If this occurs, this needs to be recorded (date and reason), and the decision can then be made to either:

- Discontinuation due to improvement in symptoms (including wound healed). Participant will still continue to be assessed as per planned dates and timepoints.
- Change over to an alternative compression bandage that is not the originally allocated type. This is allowed but only if there are clinical indications to do so or at patient request if they cannot tolerate the allocated bandage type. Patient can later in trial period be transferred back to original allocated bandage type if required.
- Pausing or discontinuation of compression bandaging when not clinically indicated. Even if leg ulcer persists and patient no longer wears compression bandage, they can still continue in the trial if they wish. Outcome measures will continue to be recorded as per planned dates and timepoints.
- Pause of compression therapy due to adverse event. Patient can remain in trial provided they are capable to continue with follow-up schedule and completion of outcome measures. If not possible, see next point regarding 'Withdraw patient from study'.
- Withdraw patient from study.
  - At the request of the patient
  - For clinical reasons, eg if the leg has deteriorated to such an extent that emergency surgical or medical intervention is required which means return to use of compression bandage in reasonable time frame is not feasible. In this case, this needs to be reported as a (Serious) Adverse Event if discontinuation is due to deterioration of the index wound or index leg only.

When overall trial participation for a patient is finished early, the participant will still be asked to complete the relevant questionnaires (provided they have capacity to do so):

- Week 6 VEINES QoL questionnaire (if patient withdrawal before week 6)
- Week 12 VEINES QoL questionnaire (if patient withdrawal > week 6 and < week 12)

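### The two causality categories in section 7.3 do not cover every event and code a possible bandage contribution as unrelated, so bandage-related events can only be under-counted

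*Protocol*

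**What the plan says.** Section 7.3 sets a compulsory rule: "The relationship of each adverse event to the trial must be determined by a medically qualified individual according to the following definitions". Two definitions follow.

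- *Related* has two conditions, given as separate sentences: "The adverse event follows a reasonable temporal sequence from intervention", and "It cannot reasonably be attributed to any other cause".
- *Not Related* has one: "The adverse event is probably produced by the participant's clinical state or by other modes of therapy administered to the participant".

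Neither section 7 nor Appendix 2 gives a third category, a tie-break or a default. Section 7.2 defines an adverse event by reference to the device and makes clear that a causal link is not required. Section 7.1 says that any adverse event will be recorded. The reporting rule for serious events is also independent of causality: "All SAEs need to be reported to the sponsor/host Trust R&D within one working day".

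**The concern.** A compulsory two-way classification should place every event in exactly one category, and an event to which the product may have contributed should be distinguishable from one to which it did not. The first category here requires the bandage to be the only reasonable explanation. The second requires another explanation to be the probable one. Between these lies the ordinary situation of two plausible causes.

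That situation is to be expected in this population. The Introduction says that the commonest unwanted effects of compression are on the skin. Section 6.2.1 admits patients with diabetes, rheumatoid arthritis and peripheral vascular disease. Section 8.1 records eczema, psoriasis, other dermatitis and skin products used on the index leg. Appendix 2 foresees that a participant may "Develop a reaction to the allocated dressing/bandage", and a competing explanation for such a reaction will often be arguable.

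At stake is the causality coding of adverse events and any comparison of related events between the arms. That has some weight because the Introduction gives comfort and less itching as part of the rationale for the Andoflex bandage. The judgement is made when each event is assessed. A statistical analysis plan cannot later recover a view of possible contribution that the form never asked for.

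**Working it through.** The protocol gives no figure on this point, so the check is logical. The inputs are the two definitions in section 7.3.

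**Step 1: are the categories exclusive and exhaustive?** Take an event with plausible timing and vary the strength of the best alternative explanation.

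| Case | Other cause | Meets *Related*? | Meets *Not Related*? | Result |
|---|---|---|---|---|
| (a) | None reasonable | Yes | No | *Related* |
| (b) | Reasonable, not probable | No | No | Fits neither |
| (c) | Probable | No | Yes | *Not Related*, even if the bandage may have contributed |

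No event can meet both definitions, because a probable other cause is also a reasonable one. The categories are therefore exclusive but not exhaustive. Itch, redness or dermatitis under the bandage in a patient with venous skin changes or eczema can fall in (b) or (c). Events with implausible timing and no probable other cause also fit neither definition, but the right answer there is not in doubt.

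**Step 2: direction.** Let *a* and *b* be the numbers of events in cases (a) and (b), and *c\** the number in case (c) for which a bandage contribution is a reasonable possibility. I take plausible timing without a probable alternative to be enough for a reasonable possibility.

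- Reasonable-possibility standard: related = *a* + *b* + *c\**.
- Section 7.3: related = *a* if every case (b) event is put under *Not Related*, and at most *a* + *b* if assessors put them all under *Related*.
- Shortfall: between *c\** and *b* + *c\**, never below zero.

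The sign holds in each arm however assessors deal with case (b). The protocol gives no value for *a*, *b* or *c\**, so the size is unknown. The shortfall could differ between arms, so no direction follows for the between-arm difference.

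**Step 3: related to what?** Three reference points appear: the device (section 7.2), the trial (opening rule of section 7.3) and the intervention (definition of *Related*). Sections 5.2 and 7.1 say that patients would receive Lite compression outside the trial too. An assessor who reads the question literally could therefore call a bandage effect unrelated to the trial. Appendix 2 also lets a participant change to another bandage and back, so the product being judged is not always the allocated one.

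**The case against.** The strongest reply is that little in the protocol rests on the label.

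- Capture of events is independent of causality (sections 7.1 to 7.3), and all-cause events can be compared by randomised arm without any attribution.
- Skin tolerance is measured directly. Pain and itch scales are taken at weeks 0, 6 and 12 (section 5.3) and compared between arms (section 8.3). Infection rates, and withdrawals due to a change in management, are secondary outcomes (section 5.5.2). Stopping or pausing the bandage is recorded with date and reason (Appendix 2).
- No endpoint or planned analysis shown uses *Related*.
- The assessor is medically qualified, and the word *reasonably* leaves room for judgement. New dermatitis confined to the bandaged skin, in a patient without previous skin disease, could qualify as *Related*.
- A default to *Not Related* is nowhere stated. It follows from the text for case (c); for case (b) it is only a likely result of having two boxes.
- The bandage is the only intended difference in care, so the trial and the device come to nearly the same thing.

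All of this stands as a limit on the consequence, except that the last reply is weaker where a participant has switched bandage. None of it closes the gap in case (b) or alters the coding in case (c).

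A reader might infer more: that related events would be close to nil in both arms, or that the trial loses its safety signal. The points above rule that out. A reader might also try to size the problem from the Introduction's statement that "pruritus develops in as many as 1 in 3 patients", as 92 × 1/3 = 30.7 patients. That is a background frequency of a symptom under compression. It counts neither adverse events nor misclassified ones, and nothing says that itch scored as an outcome is also logged as an adverse event. The Introduction in fact lists itch as an effect of the bandaging, which is hard to square with a claim that none of it could be coded *Related*.

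**Conclusion.** The point holds as a defect in a stated rule, not as missing detail. Section 7.3 leaves some events without a category and codes others as unrelated although the bandage may have contributed. Relative to a reasonable-possibility standard, the count of related events can be too low and cannot be too high. This assumes that assessors apply the two definitions as written, apart from whatever they do with case (b). The size is unknown.

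The effect is limited to causality coding and to any by-arm report of related events. The primary healing result, the recording of events, the reporting of serious events, and the itch, pain and infection outcomes are untouched. The differing reference points are a smaller part of the same problem and should be reconciled with it. The correction is worth making before events are coded, because the missing judgement is hard to reconstruct afterwards.

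**What to change.** In section 7.3 and on the adverse event form:

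1. Define *Related* as a reasonable possibility that the bandage worn at the time caused or contributed to the event.
2. Define *Not Related* as no such reasonable possibility.
3. Ask for the relationship to that bandage instead of to the trial, in line with section 7.2.

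The second definition is then the complement of the first, so every event fits exactly one category.

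The cost is two redrafted sentences and a change to the form. Sample size, primary analysis and patient care are unaffected. The downside is that more events will be labelled related, some of them with only a modest case for a bandage contribution.

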## 8. STATISTICAL CONSIDERATION AND DATA ANALYSIS PLAN

## 8.1 Analysis of baseline characteristics

To determine the demographics and characteristics of the patients, the following baseline data will be collated:

Patient details

- Age
- Sex
- Height, Weight, BMI
- Smoking status
- Postcode (deprivation score)
- Mobility status: does not walk / walks with assistance (stick/frame) / walks without assistance.

Medical history and status:

- Significant comorbidities, including CEAP Clinical score, Peripheral Arterial Disease, Diabetes (type I, type II, +/- neuropathy), Heart failure, Eczema, Rheumatoid Arthritis, Psoriasis, Other dermatitis, , Multiple Sclerosis, Cancer
- Any previous leg ulcers within last 2 years.

Index leg and ulcer status

- Leg ulcer aetiology determining need for compression bandaging
- ABPI (within last 3 months)
- CEAP Clinical score.
- Compression therapy prior to enrolment, and duration of compression (if applicable)
- Ulcer location: above calf / calf / below calf (gaiter) / spanning malleolar region / predominantly below malleolar region
- Chronicity of ulcer (in weeks)
- Ulcer size (PUSH score / measuring grid)
- If leg ulcer healed at week 6, status of index location at week 12 (ie any recurrence of ulcer?)

Compression care characteristics

- Location of regular leg care: home (self-care) / home (district nurse) / GP practice / secondary care (hospital)
- Frequency of care (change of compression bandaging: .... per week.
- 'Prescribed' compression length of time / per day: .... hours/day (<6hrs / 6-12 hrs/ 12-24hrs/ continuously)

- Specific dressing used on wound ? yes/no (if yes, which?)
- Skin care product used on index leg before application of compression bandaging?
  - o No
  - Yes, namely: eg Sudocrem, Desitin, or other cream/ointment/paste/emollient

Any differences in distribution will be established with Chi-squared test or ANOVA as indicated.

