#### 6. SUBJECTS

#### 6.1 Anticipated number of research subjects

Locally, we have healing data available from two previous trials involving venous leg ulcers, namely the PREVUE and APRICOT trials (Jonker et al 2020a, and Jonker et al 2020b). One caveat is that those

studies concerned pure venous leg ulcers and that compression bandaging could be full (40 to 50mmHg) or Lite (20 to 30 mmHg). Nonetheless, from these studies we know that the study followup time points are valid and APRICOT compared Andoflex vs Coban2.

Below a summary is given for the sample size needed. The primary outcome, wound status (healed vs non-healed) is used for sample size calculation. The non-inferiority related sample size calculation has been performed using the calculator at https://www.sealedenvelope.com/power/binary-noninferior/. Power calculations for sample size assume 80% power and 2.5% one-sided confidence interval. The non-inferiority limit is set at 15% in favour of the Coban2 control bandage. The result is shown in Table 4. Since some patients may withdraw over the course of the 12-week trial period, a 10% dropout rate is calculated into the sample size. A 1:1 allocation to the two types of compression bandage will be applied.

	Sample size calculation	
	Intervention Bandage (Andoflex)	Control Bandage (Coban2)
Ulcer healed	65%	50%
Ulcer not healed	35%	50%
	Sample size required without any du Sample size with 10% attrition rate Total of 92 patients: - 46 Patients to receive Ando - 46 Patients to receive Coba	flex

Table 4, Sample size calculations

The CONSORT guidelines require a statement on the number of patients assessed for eligibility (Schulz, Altman & Moher 2010). The number of patients screened but who did not meet the inclusion criteria or who declined to participate will be recorded, as will any patients who are lot to follow-up (Appendix 5).

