## 6.1.1 Randomisation and Blinding

Following written consent patients will be allocated at random to the one of two treatment arms, using a non-restricted randomised sequence generated for the whole sample using a free ware randomisation programme, see https://www.sealedenvelope.com/. The randomisation will be stratified by ulcer size, with one group being those with a PUSH score of up to and including 10, or a PUSH score of 11 or higher.

Each next randomisation allocation will be obtained from the sealedenvelope.com account for this PEACH trial. The randomisation will be stratified by ulcer size, with one group being those with a PUSH score of up to and including 10 (LOW PUSH randomisation), or a PUSH score of 11 or higher (HIGH PUSH RANDOMISATION).

Each next randomisation allocation will be obtained from either the LOW PUSH or HIGH PUSH the sealedenvelope.com account for this PEACH trial. The PUSH score is done as part of standard clinical practice and is a swift method (appr. 1 minute to obtain).

Since it will not be known up front how many patients will be LOW PUSH or HIGH PUSH, a total of 60 randomisations will be generated for each stratification, in blocks of 10 randomisations within said stratification. This means 6x10 randomisations for LOW PUSH and also 6x10 randomisations for HIGH PUSH. If one of the stratifications reaches 60 then only the other stratification can be recruited into going forward. It is recognised that random selection does not guarantee representativeness but variables which may affect the outcome variable are more likely to be balanced out and reliability enhanced (Thomas 1990).

As the study involves different looking bandages, it is not possible to achieve blinding for the participants. However, statistical analysis is carried out blinded to group allocation, by persons who have not had contact with study participants.

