## 8.2 Primary outcome statistics

The primary objective for this pilot study wound healed status at week 12. For non-inferiority analysis, patients who withdraw prior to completion of the study or do not attend week 12 appointment will be assigned the worst-case healing outcome (not healed at week 12).

The test for non-inferiority concerns the proportion of patients attaining ulcer closure by week 12 for both treatment groups, and the associated 97.5% one-sided confidence interval for the difference. Non-inferiority of Andoflex is considered valid if the lower limit of the 95% confidence interval for the difference between treatment means (Andoflex – Coban2) is not more negative than -15%. That is, non-inferiority for Andoflex is demonstrated when a maximum of 15% fewer patients using this bandage, compared with patients using Coban2, have healed by week 12 of treatment. This approach was taken in previous non-inferiority trials for ulcers (Harding et al, 2012; Moffatt et al, 2019), and is outlined in papers by Oczkowski (2014) and Flight (2016).

For comparative performance (superiority) analysis, any statistically significant difference (p-value < 0.05) between the two treatment arms will be determined with Chi-squared test. This will be done since Dunn et al postulate that non-inferiority and superiority trials effectively aim to answer the same hypothesis (Dunn et al, 2018)

Analysis will be performed on a per protocol and also an intention to treat basis. Multiple imputation (default five imputations) will be applied for missing values for the outcome measures, and inferential statistics will be performed on pooled data. Data will first be collated in Microsoft Excel, followed by analyses performed using SPSS v20.

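### Section 8.1 prescribes significance tests on about 32 baseline variables in a randomised trial and lists a week-12 recurrence item among them: likely spurious findings, with no effect on the primary analysis

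*Protocol*

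**What the plan says.** Protocol section 8.1 introduces its list with the statement that "the following baseline data will be collated". The list covers patient details, medical history, the index leg and ulcer, and compression care. It closes with one instruction for all of it: "Any differences in distribution will be established with Chi-squared test or ANOVA as indicated". No significance level, comparison groups or rule for multiple tests is given there.

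Under index leg and ulcer status, the list includes: "If leg ulcer healed at week 6, status of index location at week 12 (ie any recurrence of ulcer". Neither section 5.5.2 (secondary outcome measures) nor section 8.3 (secondary outcome statistics) lists recurrence.

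Section 6.1.1 states that "Following written consent patients will be allocated at random to the one of two treatment arms" and that "The randomisation will be stratified by ulcer size", with a PUSH cut-off between 10 and 11. Section 6.1 adds that "A 1:1 allocation to the two types of compression bandage will be applied".

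**The concern.** Randomisation makes the null hypothesis of each between-arm baseline test true by design, provided the items are recorded before allocation. A small p-value then cannot establish a difference in the sense that the sentence intends; it only flags a chance imbalance. Over a list of this length, one or two such flags are to be expected. A report that calls them established differences gives readers a reason to re-explain the healing result by something that is chance.

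The recurrence item raises a separate problem. Week-12 status of an ulcer that had healed by week 6 cannot be known at baseline. It is observed only in patients healed at week 6, and the bandage may influence who they are. If one arm heals more ulcers, or harder ones, by week 6, the week-6 healers in the two arms are no longer comparable groups. Read literally, section 8.1 would test this item between arms and report it as a baseline characteristic.

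**Working it through.** The plan states no error rate for these tests, so there is no figure of its own to reproduce.

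**Step 1: count the variables in section 8.1.**
- Patient details: age, sex, height, weight, BMI, smoking, deprivation score, mobility = 8.
- Comorbidities: 10 named items, including the CEAP score ("Significant comorbidities, including CEAP Clinical score, Peripheral Arterial Disease, Diabetes (type I, type II, +/- neuropathy), Heart failure, Eczema, Rheumatoid Arthritis, Psoriasis", then other dermatitis, multiple sclerosis and cancer).
- Previous leg ulcers = 1.
- Index leg and ulcer: aetiology, ABPI, CEAP again, prior compression, its duration, location, chronicity, PUSH, grid size, week-12 recurrence = 10.
- Compression care: location, frequency, prescribed time, wound dressing, skin care product = 5.

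Total: 8 + 10 + 1 + 10 + 5 = 34. Removing the repeated CEAP score and the recurrence item leaves 32.

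**Step 2: significance level.** Section 8.1 gives none. The only p-value threshold in the Protocol is in section 8.2, for the superiority comparison: "any statistically significant difference (p-value < 0.05) between the two treatment arms will be determined with Chi-squared test". I assume 0.05 two-sided for the baseline tests as well.

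**Step 3: expected false differences.** 32 × 0.05 = 1.6. This does not depend on correlation between the tests.

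**Step 4: chance of at least one, independent tests.** 1 − 0.95^32 = 0.806. Counting differently, 28 variables give 1 − 0.95^28 = 0.762 and 34 give 1 − 0.95^34 = 0.825.

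**Step 5: correlated tests.** Suppose the 32 test statistics are normal with a common correlation ρ. The chance is then 1 − E{[Φ((1.96 − √ρ·U)/√(1−ρ)) − Φ((−1.96 − √ρ·U)/√(1−ρ))]^32}, with U standard normal.

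| ρ | Chance of at least one p < 0.05 |
|---|---|
| 0 | 0.81 |
| 0.2 | 0.74 |
| 0.5 | 0.52 |

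**Step 6: cross-check by simulation.** Null data were simulated with 46 per arm and 32 mixed variables (t-test, which equals two-group ANOVA, and uncorrected Chi-squared; 1,500 replicates; variable distributions assumed). The chance of at least one was 0.79 with no common factor, 0.77 at a common correlation of 0.2 and 0.70 at 0.5, with about 1.6 false differences on average each time. Here the correlation was placed on the underlying variables. Cutting these into categories weakens it, which probably explains why 0.70 exceeds the 0.52 of Step 5.

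**Step 7: how far this is from near certainty.** A 95% chance would need about 59 independent tests: 1 − 0.95^59 = 0.952, against 1 − 0.95^58 = 0.949.

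**Step 8: what depends on these tests.** The primary analysis in section 8.2 is a difference in healing proportions with a confidence interval, without adjustment chosen from baseline tests. The Cox covariates in section 8.3 are named in advance. No eligibility rule, analysis set or decision rule refers to a baseline p-value.

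**The case against.** The strongest reply is that nothing follows from these tests. As Step 8 shows, no analysis is selected by them, so one or two chance p-values in a baseline table are a matter of reporting style. This stands, and it limits the severity.

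The reply can also press on the figure. The 0.05 level is borrowed from section 8.2. Height, weight and BMI are related, as are PUSH score and grid size, and stratification on PUSH makes a false signal on ulcer size less likely. Rare conditions seldom reach significance: at an assumed 2% prevalence with 46 per arm, uncorrected Chi-squared rejects about 1% of the time, not 5%. All of this stands. A reader who sees 32 uncorrected tests might infer that a false imbalance is near certain; the calculation does not support that. Nor does the Protocol claim any familywise error rate for baseline data.

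On recurrence, a reader might infer that the plan deliberately compares recurrence between arms among early healers and draws a treatment conclusion from it. The text does not say so. It has no recurrence hypothesis, the tests apply only as indicated, and the bullet may simply be a misplaced data-collection item. Recurrence can be observed only in ulcers that healed, so recording it conditionally is natural. Week-12 wound status is collected for every participant under sections 5.3 and 5.4 and is the primary outcome, so the restriction touches this one item. What remains is that the item sits in a list called baseline data, under a sentence that prescribes tests for that list, and has no place among the outcomes.

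**Conclusion.** The point holds as a minor one. Section 8.1 positively instructs significance testing of baseline variables in a randomised trial, so this is more than a detail left for a statistical analysis plan. With 32 variables and an assumed level of 0.05, 1 to 2 false differences are expected, and the chance of at least one is roughly 50% to 80% depending on correlation. The figures rest on that assumed level, on reading the comparison as one between the two arms, and on the assumed correlation structure.

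The recurrence item is misclassified on the face of the document. Whether a between-arm test of it was intended is not stated; read literally, section 8.1 would produce one in a group not protected by randomisation.

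It would be wrong to infer that the non-inferiority conclusion is compromised. The primary analysis, its error rate and the Cox covariates do not depend on any of this. The effect is confined to reporting and to interpretation of secondary results.

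**What to change.** 1. In section 8.1, delete the sentence prescribing Chi-squared or ANOVA. Describe baseline data by arm without p-values: counts and percentages, and mean with SD or median with IQR.
2. Move the recurrence bullet from section 8.1 to the secondary outcomes in sections 5.5.2 and 8.3. Report the number of recurrences by arm descriptively, with the number healed at week 6 as the stated denominator.
3. If a between-arm comparison is wanted, base it on all randomised patients, for example the proportion healed at week 6 and still healed at week 12, with a 95% confidence interval for the difference. State that this measures sustained early healing rather than recurrence itself. It would be an added secondary summary, so it is optional.

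The cost is wording in sections 5.5.2, 8.1 and 8.3. No extra data or patients are needed, because wound status is already recorded at weeks 6 and 12, and the number of tests falls.
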